15.3 Evaluation of Potential Effect of ADA/nAb on Bintrafusp alfa Efficacy

Analysis Sets: Immunogenicity analysis set

Following analysis will be described by subgroup of ADA (never positive/ever positive) and nAb (never positive [ie: no PD-L1 positive assay and no TGF β positive assay at any timepoint including baseline]/ever positive [ie either PD-L1 or TGF β positive assay at any timepoint including baseline]):

- Confirmed BOR per Investigator as described in Section 14.1.1 for dose escalation cohorts

- Confirmed BOR per Investigator and IRC as described in Section 14.1.1 and Section 14.1.2 for dose expansion cohorts
- PFS per Investigator as described in Section 14.3 for dose escalation cohorts and respective Kaplan-Meier curve
- PFS per Investigator and IRC as described in Section 14.3 for dose expansion cohorts and respective Kaplan-Meier curve
- OS as described in Section 14.4 and respective Kaplan-Meier curve
- Listings of efficacy assessments and immunology parameters for ADA positive subjects will include: cohort, participant identifier, age, sex, ADA and nAb categories, date of first study treatment, treatment duration, cBOR, PFS, time to response, DR and OS. Subjects with treatment ongoing or response ongoing will be flagged.

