8.1 Definition of Analysis Populations

Screening Analysis Set (SCR): All participants who signed the informed consent form.

Full Analysis Set (FAS) / **Safety Analysis Set (SAF):** All participants who received at least 1 dose of trial treatment (> 0 mg and/or duration of infusion > 0). The SAF terminology will be used for the safety analysis and the FAS terminology will be used for efficacy analysis.

PK Analysis Set (PKAS): All participants who complete at least 1 infusion of trial treatment, and who provide at least one post-dose sample with measurable concentration of bintrafusp alfa.

PKADA is defined as a subpopulation of the PK Analysis Set and restricted to participants who have in addition at least one valid result of antidrug antibody (ADA) at any time point.

PKNAB is defined as a subpopulation of the PK Analysis Set and restricted to participants who have in addition at least one valid result of nAb at any time point.

Immunogenicity Analysis Set (IMM): All participants who received at least 1 dose of trial drug and who have at least one valid result of ADA (i.e. ADA is negative, or positive with or without the titer result available) at any time point.

The analysis of efficacy and safety by nAb will be performed if we have nAb data for at least 5 participants.

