14.3 Progression-Free Survival

Progression-Free Survival (PFS) time is defined as the time (in weeks) from first administration of trial treatment until the first date of PD or death due to any cause within 84 days (12 weeks) of last tumor assessment if death occurred during the treatment period, or within 168 days (24 weeks) of last tumor assessment if death occurred during the follow-up period.

PFS will be censored in the following scenarios:

- Participants who do not experience an event (PD or death) will be right-censored on the date of the last evaluable (non-missing and non "Not Evaluable") tumor assessment.
- Participants who start new anti-cancer treatment prior to an event will be censored on the date of the last evaluable (non-missing and non "Not Evaluable") tumor assessment before anti-cancer therapy is given.
- Participants with an event after two or more subsequent missing response assessments (i.e. 2 times the scheduled time interval between two subsequent response assessments) will be censored on the date of the last evaluable (non-missing and non "Not Evaluable") tumor assessment.
- Note: 2 times the scheduled time interval means 84 days during the treatment period and 168 days during the follow-up period (for participants who ended the treatment not for progression)
- Participants who do not have a baseline tumor assessment or who do not have any postbaseline tumor assessments will be censored on the date of first dose unless death occurred on or before the time of the second planned tumor assessment in which case the death will be considered an event.

PFS = (date of PD or death/censoring - date of the first dose + 1)/30.4375 (months).

PFS event / censoring are defined in Table 3:

Table 3 Progression-free Survival Event / Censoring

PFS Event Stat	PFS Event Status		Date of event / censoring
Progressed or died Within two subsequent scheduled tumor assessments after last response assessment of CR, PR or SD		Event	Minimum (Date of PD, Date of death)
	Otherwise	Censored	Date of last tumor assessment with outcome CR, PR or SD or date of first dose, whatever is later
Neither progressed nor died		Censored	Date of last tumor assessment with outcome CR, PR or SD or date of first dose, whatever is later

CR = complete response; PD = progressive disease; PFS= progression-free survival; PR = partial response; SD = stable disease.

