14.4 Overall Survival

The overall survival (OS) time is defined as the date from first dose to death due to any cause:

OS = (date of event/censoring - date of the first dose + 1)/30.4375 (months).

For patients alive at the time of data cut-off date or who are lost to follow up, OS will be censored at the last date known to be alive.

The date of event / censoring is defined in Table.

Table 4 Survival Event / Censoring

	Date of event / censoring	Censoring
Participants alive or lost to follow-up before or at cut-off date	Last date known to be alive	Yes
Participants who died before or at cut-off date	Date of death	No

- All patient assessment dates (blood draws (laboratory, PK), vital signs, performance status, ECG, tumor assessments, quality of life assessments)
- Start and end dates of anti-cancer therapies administered after study treatment discontinuation.
- AE start and end dates
- Last known alive date in the "Survival Follow-Up" eCRF
- Study drug start and end dates
- Date of discontinuation from the "Study Termination" eCRF page (do not use if reason for discontinuation is lost to follow-up or death)

The last known to be alive date will be completed by the date of death for dead participants.

The analysis of OS will be performed with a Kaplan-Meier method (product-limit estimates) and a summary of associated statistics will be presented including corresponding two-sided 95% CIs. The CIs for the median will be calculated according to Brookmeyer and Crowley (1982) and CIs for the survival function estimates at Month 3, 6, and 12, 18, 24, 36, and 48 months (depending on actual data) will be derived using the log-log transformation according to Kalbfleisch and Prentice (1980) (CONFTYPE=loglog default option in SAS PROC LIFETEST). The estimate of standard error will be computed using Greenwood's formula. OS rates with their CI at 3, 6, 12, 18, 24, 36 and 48 months will be presented, as well as the number of participants at risk and failed.

A participant listing will provide the following information: dose level/cohort, participant identifier, age, sex, MSI status, PD-L1 expression, date of first administration, date of last tumor assessment, date of event/censoring, event/censoring reason, time to event.

14.5 **Subgroup Analysis**

BOR, DR, PFS according to RECIST 1.1 by Investigator and IRC, as well as OS analyses will be performed on subgroups as shown below:

Table 4 Efficacy assessments by subgroups

	BOR		PFS		DR ^a		os

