	Inv	IRC	Inv	IRC	Inv	IRC	
BTC classification			✓	✓			✓
PD-L1 TC ^b	✓	✓	✓	✓	✓	✓	✓
PD-L1 TME ^b		✓		✓		✓	✓

PD-L1 WTU ^b		✓		✓	✓	✓
MSI		✓				
ADA	✓	✓	✓	✓		✓
nAb	✓	✓	✓	✓		✓

^a Only for dose expansion participants (excluding HCC)

ADA = antidrug antibody; BOR = best overall response; BTC = biliary tract cancer; DR = duration of response; HCC = hepatocellular carcinoma; Inv = Investigator; IRC = Independent Review Committee; MSI: Microsatellite Instability; nAb = neutralizing antibody; OS = overall survival; PD-L1 = programmed death ligand 1; PFS = progression-free survival.

Corresponding Kaplan-Meier figures will be provided for PFS, DR and OS. For BOR, corresponding spider plot will be displayed.

Patients with missing subgroup will not be included in analyses.

15 Anti-Drug Antibody and Neutralizing Antibody

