15.1 Anti-Drug Antibody

Analysis Sets: Immunogenicity analysis set

Anti-drug antibody (ADA) will be assessed before the trial treatment start, and on Days 15, 29, 43, 57, 71, and 85 after the start of infusion, 6-weekly up to/including Week 25, every 12 weeks after Week 25, and during safety follow-up (the term HAHA is used in the eCRF). Samples collected after the on-treatment period (e.g. safety follow-up) will be included in the analysis as well. If the sample is positive for ADA, it will be re-analyzed to determine the titer. The ADA results will be derived based on the algorithm in Table 5.

Table 5 Algorithm for the Derivation of ADA Results

Sample Screen Result	Confirmatory	Titer	ADA Result
Negative	NA	NA	Negative
NR	NA	NA	NR
Positive	Negative	NA	Negative
Positive	NR	NA	NR
Positive	Positive	Number	Number
Positive	Positive	NR	Positive-TNR

NR = no result, NA = not applicable, TNR = titer no result.

Negative, number, or positive-TNR are valid results while number and positive-TNR are considered as positive. Participants will be characterized into different categories based on the criteria in

Table 6 below.

Table 6 Participants Characterized based on ADA Results

^b 1% cutoff

Category	Definition	Participant at Risk (Denominator for Incidence)
Never positive	No positive results at any time point	Number of participants with at least one valid result at any time point
Ever positive	At least one positive result at any time point, including baseline	Number of participants with at least one valid result at any time point
Pre-existing	A positive ADA result prior to treatment with bintrafusp alfa	Number of participants with valid baseline result
Treatment boosted	A positive ADA result prior to treatment with bintrafusp alfa and the titer ≥ 8*baseline titer at least one post-baseline value	Number of participants with valid baseline result and at least one valid post-baseline result
Treatment emergent	Not positive prior to treatment with bintrafusp alfa and with at least one positive post-baseline result	Number of participants with at least one valid post-baseline result and without positive baseline result (including NR)
Transient positive	If treatment emergent participants have (a single positive evaluation, or duration between first and last positive result <16 weeks) and last assessment not positive.".	Number of participants with at least one valid post-baseline result and without positive baseline result (including NR)

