15.4 Evaluation of Potential Effect of ADA/nAb on Bintrafusp alfa Safety

Analysis Sets: Immunogenicity analysis set

The following analyses frequency and percentage of AEs by ADA subgroups and nAb (never positive [i.e. no PD-L1 positive assay and no TGF β positive assay at any timepoint including baseline]/ever positive [i.e. either PD-L1 or TGF β positive assay at any timepoint including baseline]) will be performed in each cohort (refer to Section 16):

- TEAEs
- TEAEs, grade ≥ 3
- TEAEs leading to permanent treatment discontinuation
- TEAEs excluding IRRs leading to drug interruptions
- Serious TEAEs
- TEAEs leading to death
- irAEs
- IRRs
- Skin AESI
- Anemia (using the search preferred term 'Anaemia')

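### Ever/never ADA and nAb positivity, set by samples taken at any later time, is used to split PFS and OS curves that start at first dose, so in expectation the curves favour ever-positive subjects

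*SAP*

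**What the plan says.** **Status.** SAP 15.1, Table 6, defines ADA ever positive as "At least one positive result at any time point, including baseline". On late samples it adds: "Samples collected after the on-treatment period (e.g. safety follow-up) will be included in the analysis as well". For nAb, SAP 15.3 counts a positive in either assay at any timepoint.

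**Population.** The immunogenicity set in SAP 8.1 is "All participants who received at least 1 dose of trial drug and who have at least one valid result of ADA", at any time point. No post-baseline sample is required.

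**Outcomes.** SAP 14.3 and 14.4 compute PFS and OS from the date of first dose. SAP 15.3 sets the grouping: "Following analysis will be described by subgroup of ADA (never positive/ever positive) and nAb". It asks for confirmed BOR, PFS and OS by ever/never status, with Kaplan-Meier curves for PFS and OS. The ADA and nAb rows of the table in SAP 14.5 repeat this, and the text below that table says: "Corresponding Kaplan-Meier figures will be provided for PFS, DR and OS". SAP 15.4 begins: "The following analyses frequency and percentage of AEs by ADA subgroups"; these are crude percentages over an on-treatment window that ends 30 days after last dose or at new anticancer therapy (SAP 9.7).

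**Use of timing.** SAP 15.1 and 15.2 define the date of first positive and summarise time to it. They also list each responder's response date relative to it. SAP 17.3 summarises and plots Ctrough by day relative to seroconversion. No landmark or time-dependent analysis is given for PFS or OS.

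**The concern.** The grouping uses information that arises after the clock has started. A subject with a negative baseline sample who dies on Day 10 is never positive by definition, because the first post-baseline ADA sample is on Day 15. A subject can be a treatment-emergent positive only by surviving, and remaining under sampling, until a positive sample is drawn. Early progressors and early deaths therefore collect in the never-positive group whether or not antibodies matter.

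At stake is the question that SAP 15.3 sets out to answer. If antibodies did reduce efficacy, the built-in advantage of the ever-positive group would offset the loss, and the curves could look reassuring. SAP 4 allows the planned analyses to appear in regulatory submissions or manuscripts, so the curves could be read in that way later.

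**Working it through.** The plan states no hazard ratio, event count or ADA rate for this comparison, so there is no figure of its own to reproduce.

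**Direction, by algebra.** Suppose conversion time C (rate λ) and PFS time T (rate μ) are independent exponentials, and status is observed up to the event.

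- Mean T given C > T (never positive): 1/(λ+μ).
- Mean T given C < T (ever positive): 1/(λ+μ) + 1/μ.

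The gap is 1/μ although C has no effect on T. With an assumed median of 2.5 months, 1/μ = 2.5/0.693 = 3.6 months. Samples after progression, which the SAP admits, soften this gap but do not remove it.

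**Worked example with the protocol's sampling.** From the documents:

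- ADA on Days 15, 29, 43 and 85, then 6-weekly to Week 25, then 12-weekly (protocol Table 3, GC/ESCC/BTC);
- further samples 28 days and 10 weeks after last dose;
- 6-weekly scans.

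Assumed: median time to progression 2.5 months, median post-progression survival 7 months, 30% seroconverting by 24 weeks (rate −ln(0.70)/168 = 0.0021 per day), no baseline positives, treatment to PD or 12 months, true hazard ratio 1, 6,000 subjects.

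| Analysis | PFS HR | OS HR |
|---|---|---|
| Fixed ever/never, from first dose | 0.63 (medians 4.1 vs 2.8 months) | 0.73 (13.4 vs 9.8 months) |
| Time-dependent status | 0.97 | 0.94 |

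The mean on-treatment window was 194 days (ever) against 140 (never). Over 18 scenarios (median time to progression 1.5 to 4 months, 15 to 50% converting, 0 or 5% baseline positives), the fixed split gave PFS 0.52-0.79 and OS 0.69-0.82. Time-dependent status gave 0.93-1.09 and 0.94-1.03.

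**Sensitivity to onset.** A larger null simulation (100,000 subjects per scenario; median PFS 2, 3 or 4 months; 15, 30 or 50% convertible) varied onset:

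| Assumed onset | PFS HR | OS HR | PFS HR with 10% baseline positives |
|---|---|---|---|
| A minority, all within 6 weeks | 0.89-0.97 | 0.87-0.97 | 0.90-0.99 |
| Gradual, median 112 days | 0.63-0.80 | 0.72-0.81 | 0.69-0.89 |

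Constant risk for everyone gave stronger bias (PFS 0.38-0.67). SAP 15.1 lists Days 57 and 71, which protocol Table 3 omits for expansion; including them moved the PFS limits by at most 0.02.

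**Noise in one cohort.** At 30 subjects, median PFS 3 months and 30% convertible, the 95% range of the null PFS HR was 0.39-2.63 (within 6 weeks) and 0.22-2.24 (gradual).

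**BOR and AEs, no true effect, gradual onset.** Ever against never:

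- response 25-28% vs 14-17% (true rate 18%);
- grade 3 or higher AEs 44-46% vs 28-37%;
- early discontinuation AEs 6% vs 9-11%, the reverse direction.

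**The case against.** The strongest reply is about consequence. SAP 8.2 calls all subgroup analyses exploratory, SAP 9.10 plans no tests, and SAP 6.1 records that the addendum is approved and the final analysis cancelled. Seroconversion timing is used for Ctrough, which fits the protocol's secondary objective on immunogenicity and drug exposure. SAP 15.3 also lists PFS, DR and OS with ADA and nAb categories for each ADA-positive subject. All of this stands and lowers the severity. It does not make the curves interpretable, because a descriptive curve with a built-in advantage remains biased.

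A second reply is that the remedy is weak. In single cohorts this is largely true: at 30 subjects the null time-dependent PFS HR spans about 0.4-3.2 (onset within 6 weeks) or 0.2-7.3 (gradual or constant risk). The time-dependent OS HR also keeps a residual, 0.89-1.03 in most scenarios and 0.66-1.06 if nearly everyone converts. The reason is that ADA is sampled only on and shortly after treatment, so being found positive still goes with staying on treatment.

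A reader might infer that AE rates per person-time, before and after first positive, would cure the AE tables. They would do so only if the AE hazard were constant. Protocol 3.4.1 reports that, of 49 expansion subjects with infusion reactions on the parent antibody, onset followed the first infusion in 30 and the second in 16; SAP 15.4 tabulates infusion reactions. With no true effect, doubling the hazard in the first 28 days gave an after/before rate ratio of 0.80-0.86, and a fourfold hazard gave 0.59-0.68. That is a false protective signal.

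**Conclusion.** The design flaw is real, and its direction follows from the definitions: in expectation, without a true effect, the PFS and OS curves favour ever-positive subjects. The size is unknown. Under assumed inputs the null PFS HR is about 0.9-0.97 if a minority convert within 6 weeks and about 0.65-0.8 with gradual onset. Survival times, conversion share and onset are all assumptions.

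Three stronger readings are not supported.

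- A reader might infer that the reported curves must show ever-positive subjects doing better. The bias holds in expectation only. Cohorts of 30 are noisy, baseline positives dilute it, and a true harmful effect would pull the other way.
- A reader might infer that BOR and AE tables err in the same direction. Their problem is unequal exposure and sampling, and for AEs it can go either way.
- A reader might infer that the trial's efficacy conclusions are affected. These are exploratory, untested subgroup outputs, already reported, and no primary or secondary conclusion changes.

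Severity is therefore low, and the point matters for the further use that SAP 4 foresees.

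**What to change.** For any submission or manuscript use:

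1. Do not present the ever/never Kaplan-Meier curves as evidence on the effect of ADA or nAb.
2. Add one analysis, labelled post hoc, of PFS and OS with ADA or nAb as a time-dependent covariate that switches at the first-positive date already defined in SAP 15.1 and 15.2. Report an estimate with CI and no test, and state the residual OS bias. One model stratified by cohort across the 1200 mg cohorts is an option; it departs from the cohort-by-cohort plan, so say so. Fit nAb only where the minimum of 5 participants in SAP 8.1 is met.
3. Caveat the ever/never curves and the BOR and AE tables, and place the existing time-to-first-positive summary beside them.
4. Do not use an unadjusted before/after AE rate. Any such rate must be adjusted for, or stratified by, time on treatment.

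The cost is modest programming on existing data, and wide intervals. In single cohorts the caveat will do most of the work.

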15.4 Evaluation of Potential Effect of ADA/nAb on Bintrafusp alfa Safety

Analysis Sets: Immunogenicity analysis set

The following analyses frequency and percentage of AEs by ADA subgroups and nAb (never positive [i.e. no PD-L1 positive assay and no TGF β positive assay at any timepoint including baseline]/ever positive [i.e. either PD-L1 or TGF β positive assay at any timepoint including baseline]) will be performed in each cohort (refer to Section 16):

- TEAEs
- TEAEs, grade ≥ 3
- TEAEs leading to permanent treatment discontinuation
- TEAEs excluding IRRs leading to drug interruptions
- Serious TEAEs
- TEAEs leading to death
- irAEs
- IRRs
- Skin AESI
- Anemia (using the search preferred term 'Anaemia')

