15.5 Evaluation of Potential Effect of ADA on Bintrafusp alfa PK

Bintrafusp alfa concentration in serum will be descriptively summarized as described in Section 16.3 to evaluate the potential effect of ADA on PK.

16 Safety Evaluation

Analysis set: Safety Analysis Set

All safety description will be provided per dose level/cohort and overall (dose escalation overall, HCC overall, dose expansion overall (excluding HCC)).

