16.1 Adverse Events

Treatment emergent adverse events (TEAEs) are those events with onset dates occurring during the on-treatment period for the first time, or if the worsening of an event is during the on-treatment period as defined in Section 9.7. Adverse events will be coded according to the most current version of MedDRA. Severity of AEs will be graded using the NCI-CTCAE v4.03 toxicity grading scale.

Changes in toxicity grade, seriousness or outcome of AEs are recorded as separate entries in the eCRF with associated end and start dates (start date equals end date of previous entry). Such entries reporting the same event in such immediately consecutive periods will be considered as one event in the analysis in case of a change in toxicity grade. These events will be kept as separate records in the database in order to maintain the full detailed history of the events. The start date of the initial record in the sequence is taken as start date of the entire event. Duration of the AE and the TEAE flag will be adjusted accordingly in the analysis.

All analyses described in this section will be based on TEAEs if not otherwise specified. The AE listings will include all AEs (whether treatment-emergent or not).

- **Related Adverse Events**: adverse events with relationship to study treatment (as recorded on the "Adverse Events Details" eCRF page, Relationship with MSB0011359C= Related) reported by the investigator and those of unknown relationship (i.e. no answer to the question "Relationship with MSB0011359C").
- **Serious Adverse Events (SAE)**: serious adverse events (as recorded on the "Adverse Events Details" eCRF page, Serious Adverse Event = Yes).
- Adverse Events leading to Treatment Discontinuation: adverse events leading to permanent discontinuation of study treatment (as recorded on the "Adverse Events Details" eCRF page, Action taken with MSB0011359C = Drug withdrawn).
- Adverse Events leading to Death: adverse event leading to death (as recorded on the "Adverse Events Details" eCRF page, Outcome = Fatal, as well as AEs of Grade 5).
- Adverse Events of Special Interest (AESI): adverse events of special interest (as identified according to a pre-specified search list of MedDRA Preferred Terms). Categories of AESI include:

- o Immune-Related Adverse Events (irAE)
- o Infusion-Related Reactions (IRR) including hypersensitivity
- O Skin AE possibly related to TGFβ inhibition
- o Anemia

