Anemia events are those AEs belonging to the MedDRA HLT Anaemias NEC, HLT Anaemias haemolytic immune, HLT Anaemias haemolytic NEC or PT = Haemoglobin decreased.

• **Bleeding events** are those AEs belonging to the MedDRA SMQ Haemorrhage terms (excluding laboratory terms).

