16.2.3.4 Anemia Adverse Events

The incidence of anemia will be described all dose level/cohorts combined (where applicable) and by dose level/cohort:

- Incidence by Worst Grade, SOC, and PT
- Incidence of related anemia by Worst Grade, SOC, and PT

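### The ADA/nAb safety tables search for anemia with one preferred term, while the SAP's own anemia definition covers three high-level terms plus Haemoglobin decreased, so the subgroup row would leave out any event coded elsewhere in that definition

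*SAP*

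**What the plan says.** SAP 15.4 plans counts and percentages of adverse events by ADA and nAb status. It states that these "will be performed in each cohort (refer to Section 16"), and it is run on a restricted population: "Analysis Sets: Immunogenicity analysis set". Most rows, including irAEs, IRRs and skin AESI, name only the event class and leave its definition to Section 16. The last row carries its own search: "Anemia (using the search preferred term 'Anaemia".

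SAP 16.1 lists anemia among the adverse events of special interest, which are "as identified according to a pre-specified search list of MedDRA Preferred Terms". It then defines anemia: "Anemia events are those AEs belonging to the MedDRA HLT Anaemias NEC, HLT Anaemias haemolytic immune", followed by "HLT Anaemias haemolytic NEC or PT = Haemoglobin decreased". The AESI rows of the overall summary (16.1.1) and the anemia tables (16.2.3.4) give no other definition, so this one governs them. The latter include "Incidence of related anemia by Worst Grade, SOC, and PT". Section 16 opens with a different population: "Analysis set: Safety Analysis Set".

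**The concern.** The same label, anemia, stands over two different event sets in one plan. Section 15.4 sends the reader to Section 16 and then departs from it for this row alone, without a stated reason. A reader who sets the antibody-subgroup table beside the main anemia table would take the two rows as the same endpoint.

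Anemia matters in this trial. Protocol 3.4 names it as an important risk, and Protocol 7.4.1.1.4 makes it an AESI when the investigator suspects a drug relationship. At stake is whether the table meant to show a link between antibodies and safety counts all the events that the SAP itself calls anemia.

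**Working it through.** The documents give no event counts, so there is no figure to reproduce. The check compares the two definitions.

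| | SAP 15.4 | SAP 16.1 (governs 16.1.1 and 16.2.3.4) |
|---|---|---|
| Terms | PT Anaemia | HLT Anaemias NEC; HLT Anaemias haemolytic immune; HLT Anaemias haemolytic NEC; PT Haemoglobin decreased |
| Population | Immunogenicity set | Safety set |
| Reason for the choice | None given | Stated as the definition of anemia events |

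**Step 1: which events differ.** Haemoglobin decreased is in 16.1 and not in 15.4, whatever the contents of the HLTs. Any PT in the three HLTs other than Anaemia is also in 16.1 and not in 15.4.

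**Step 2: effect on incidence within a subgroup.** Take one antibody subgroup *g* with N_g participants, and count each participant once. Let a_g be the number with at least one event coded to PT Anaemia. Let m_g be the number whose only qualifying events are coded to the other terms of 16.1. If PT Anaemia belongs to one of the three HLTs:

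- incidence under 15.4 = a_g / N_g
- incidence under 16.1 = (a_g + m_g) / N_g
- difference = m_g / N_g, which is zero or positive.

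A participant with both PT Anaemia and Haemoglobin decreased is counted either way, so m_g can be smaller than the number of omitted events. The difference is zero if no participant has only the other terms.

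**Step 3: effect on the contrast.** Moving from 15.4 to 16.1 shifts the ever-positive minus never-positive difference by m_pos/N_pos − m_neg/N_neg. Nothing in the documents fixes the sign, and the shift is zero if the two proportions are equal.

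**Step 4: is the narrow search plainly deliberate?** Where the SAP wants a narrow and a broad version of an event, as for skin events in 16.2.3.3, it defines and labels both. It has no such pair for anemia. The main anemia tables are broken down by SOC and PT, which presupposes more than one term.

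**The case against.** The strongest reply is that the narrow search is stated openly. The term is written into the row, and the row is not called an AESI although the skin row just above it is. It could be a separately defined row, and a single term is a defensible choice for an exploratory table. This stands in part: nothing is hidden. But the SAP gives no reason, and it points to Section 16 for its definitions.

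The practical weight is also small. SAP 9.10 plans no statistical tests of the study endpoints, SAP 8.2 calls all subgroup analyses exploratory, and SAP 8.1 makes the nAb safety analysis conditional on nAb data from at least 5 participants. Omitted events still enter the all-TEAE row of 15.4, the full anemia tables and the adverse event listings by participant. All of this stands and limits the point. The irAE row is not a dependable substitute, because 16.2.3.2 also requires a match to a pre-selected term list and a record of corticosteroid, immunosuppressant or hormonal treatment.

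Four stronger readings are tempting, and the documents do not support them:

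- *That events have in fact been lost.* The number may be zero. Protocol 7.4.1.1 tells sites to report the medical condition and not the laboratory value, which may make Haemoglobin decreased uncommon.
- *That the antibody contrast is biased.* The same search applies to both groups, and step 3 shows no known direction.
- *That the definition alone explains why totals would not agree with the main table.* The two tables use different analysis sets, so totals may differ even with one definition.
- *That the omitted haemolytic forms are those most relevant to an antibody effect.* Neither document says so. Protocol 7.4 links anemia to the anti-TGFβ activity.

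**Conclusion.** The inconsistency is real and minor. As written, 15.4 would leave out of its anemia row any event coded to Haemoglobin decreased, or to a PT other than Anaemia in the three HLTs, although 16.1 counts these as anemia. In the same participants the subgroup incidence can only be equal to or lower than under 16.1. The size is unknown and may be zero, and the effect on the ever-positive versus never-positive contrast has no known direction.

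The equal-or-lower statement assumes that PT Anaemia falls within one of the listed HLTs, since the SAP does not list their contents. The omission of Haemoglobin decreased does not depend on that assumption.

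**What to change.** In SAP 15.4, replace the single-term search with the anemia definition of 16.1, and rerun that row by ADA and nAb status. If the PT-only row is also kept, label it as PT Anaemia only. Because the analysis sets differ, a footnote should say that totals need not match the main anemia table.

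SAP 6.1 records that the CSR addendum is already approved, so a change of wording alone alters no output. SAP section 4 allows these analyses to be used in regulatory submissions or later manuscripts, and the rerun should come before any such use. The cost is one line of text and a small table rerun, using a definition that the SAP already applies in 16.1.1 and 16.2.3.4. No other analysis changes.
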